7.3 Duration of Participation

The participants who complete all study contacts will participate for a total of 23 weeks.

7.4 Test Article(s) (Study Drug(s) and/or Study Device(s))

7.4.1 Description

Research cigarettes (SPECTRUM) used in the study are provided by the NIDA Drug Supply Program (Notice Number NOT-DA-14-004). They are available from the Research Triangle Institute (RTI, North Carolina) with the same additives as commercial cigarettes but contain varying levels of nicotine. The cigarettes come in either menthol or non-menthol cartons. Each carton includes 10 packs of cigarettes with 20 cigarettes per pack. The physical characteristics, chemical profiles and pharmacokinetics of the research cigarettes have been well characterized (66-68).

We will use JUUL e-cigs purchased from JUUL Labs, Inc. The JUUL e-cig is a closed-system device that contains 2 main components- a disposable pod that contains liquid and a heating coil, and a USB-rechargeable battery. The disposable pods contain 0.7 mL of e-cig liquid and contain either 0% or 5% nicotine strength by weight. The device is rechargeable with a USB charging dock. The JUUL e-cig device meets battery and electrical testing standards. The safety features of JUUL include breath activation to prevent the device from turning on accidentally and a low power setting that limits its peak temperature.

We had originally proposed to use the NIDA Standardized Electronic Cigarette (SREC) because (a) it is available with a placebo matching the nicotine variety (b) it has known nicotine pharmacokinetics (mean Cmax = 17.7 ng/ml after 10 puffs in 4.5 minutes) and (c) it is known to deliver low concentrations of toxicants relative to both cigarettes and some other e-cigs(69, 70). In a laboratory study of chemicals emitted by SREC here at Penn State, we concluded that *“Overall, SREC was more efficient at aerosol and nicotine production than both Blu and Vuse. In terms of carbonyl and free radical levels, SREC delivered lower or similar levels to both other devices.”*(69) However, the e-cig company manufacturing the NIDA SREC product has experienced technical difficulties as it moved from producing small numbers of this e-cig to manufacturing a large number of e-cigs for numerous clinical trials. We cannot use this product until these problems have been resolved. Our NIH program officer agreed with us that in this ongoing situation, for this protocol (which is not required to use the SREC device), it makes sense to use JUUL.

The reasons for selecting JUUL are the same as reasons we originally selected the SREC, (a) it is available with a placebo matching the nicotine variety (b) it has known nicotine pharmacokinetics (baseline-adjusted mean Cmax = 15.4 ng/ml after 10 puffs in 4.5 minutes, as compared with 20.1 ng/ml from a Pall Mall cigarette(71)) and (c) it is known to deliver low

concentrations of toxicants relative to both cigarettes and some other e-cigs (72). Our own lab here at Penn State studied JUUL in a similar manner to SREC and concluded that *“These findings suggest that oxidative stress and/or damage resulting from JUUL use may be lower than that from cigarettes or other e-cig devices.”* Other labs, independent of JUUL, have studied the JUUL product and come to very similar conclusions: *“JUUL’s nicotine-normalized formaldehyde and total aldehyde yields are lower than other previously studied ECIGs and combustible cigarettes.”* (73). One of the key advantages of JUUL is that it has a built-in temperature-controlled circuit that prevents the temperature of the liquid from exceeding 215°C. In other e-cigs overheating of the coil as the liquid in the wick runs low is one factor suspected of causing higher toxicant emissions (but still far lower than cigarettes). JUUL’s design avoids this. Finally, in September 2019, FDA announced a new deadline for all e-cigarette manufacturers to apply for the right to continue to stay on the market (September 9, 2020). These Pre-market Tobacco Product applications (PMTAs) require all manufacturers to provide FDA with a very comprehensive set of information about their product, including marketing plans. It is likely that only the major e-cig manufacturers will be capable of submitting acceptable PMTAs to legally stay on the market after September 9, 2020. While it is impossible to know the outcome of that process, we need to select a product to use in our trial that appears likely to remain on the market in the foreseeable future, and so that is another reason for selecting JUUL.

7.4.2 Treatment Regimen

At Visit 2, all participants will be given Normal Nicotine Cigarettes (11.6 mg nicotine/cigarette) to use for 2 weeks. At Visit 3, participants will be randomized into one of the 4 arms described below:

	5% Nicotine E-cig	0% Nicotine E-cig
Normal Nicotine Cigarettes (NNCs) (11.6 mg nicotine/cigarette)	Arm 1	Arm 2
Very Low Nicotine Cigarettes (VLNCs) (0.2 mg nicotine/cigarette)	Arm 3	Arm 4

Participants will be provided with these products starting at Visit 3 (Week 0) and continue to use these products ad libitum through Visit 7 (Week 16).

7.4.3 Method for Assigning Subject to Treatment Groups

Eligible participants will be allocated to one of the four conditions using a blocked randomization with a 1:1:1:1 ratio of condition assignments via REDCap. The randomization table will be created by the study statistician and only unblinded staff will have access to it.

7.4.4 Subject Compliance Monitoring

Compliance will be monitored throughout the trial by a) daily product use logs; b) product accountability logs where the amount of product dispensed will be recorded and unused products collected and recorded; and c) questionnaires administered during study contacts regarding the use of other tobacco or nicotine products. Any problems that arise or are anticipated will be discussed and problem-solved with the coordinator. Furthermore, exhaled CO measurements will be collected throughout the study to verify smoking intensity and exposure levels.

7.4.5 Blinding of the Test Article

Research cigarettes: An unblinded staff member will receive and remove all identifiers from cigarette cartons and replace them with our own blind code labels. The blind code labels will be unique to each carton and correspond to a nicotine dose level. There are no identifiers on individual packs of cigarettes. The blinded researcher will not be involved in the packing and labelling of the research cigarettes.

E-cigs: The e-cig products will be received by unblinded staff who will appropriately package the pods and e-cig parts (device+charger) into packs/kits for the participants. The kits will have assigned numbers corresponding to a nicotine dose level, and the participants will be randomly assigned to a kit number at the randomization visit. The blinded researcher will not be involved in the packing and labelling of the kits.

All other study personnel, including lab staff, will remain blinded until the last randomized participant completes Visit 8.

7.4.6 Receiving, Storage, Dispensing and Return

7.4.6.1 Receipt of Test Article

Research cigarettes: Experimental cigarettes will be provided free of charge to the investigators via the NIDA Drug Supply Program (Notice Number NOT-DA-14-004). They will be shipped in boxes to Penn State from the Research Triangle Institute. The boxes will contain cartons of cigarettes- 10 packs in each carton with 20 cigarettes in each pack. Each carton is packaged by nicotine content and menthol (green)/non-menthol (blue) flavoring.

E-cigs: The JUUL device will be purchased from JUUL Labs, Inc. in its standard packaging and shipped to Penn State and will be received by unblinded staff. Pre-filled, sealed, disposable pods containing 0.7 mL of e-cig liquid will also be purchased from JUUL Labs, Inc. The research team will maintain the certificates of analysis or lot information for the JUUL products used in the study.

7.4.6.2 Storage

Research cigarettes: Cigarettes will be stored in standard freezers at Penn State in a locked space that is only accessible by unblinded research staff involved in our studies. A service provided by Penn State will monitor and record the temperature of the freezers.

E-cigs: Devices and e-liquids will be stored at room temperature at Penn State in a locked space that is only accessible by unblinded research staff involved in our studies. A service provided by Penn State will monitor and record the temperature/humidity of the room.

7.4.6.3 Preparation and Dispensing

All receiving, sorting, blinding of the study products will be done in secure, locked space for unblinded research staff at Penn State Hershey.

Research cigarettes: Once the cigarettes are received, they will be blinded by the unblinded study staff with unique blind codes. At Visit 3, following

confirmation of eligibility for randomization, staff will use blind codes to dispense the cartons to participants. Staff will prepare a bag of cigarette packs that will be given to the study coordinator for the participant. The blinded researchers will not be involved in the packing and labeling of the cigarettes.

E-cigs: The pods will come pre-filled in sealed packages. They will be prepared for participants by unblinded staff and stored with unique identifiers. Unblinded staff will appropriately package kits containing two JUUL devices and a supply of pods for the participants. At Visit 3, following confirmation of eligibility for randomization, participants will be randomly assigned a kit number. The blinded researchers will not be involved in the packing and labeling of the kits.

7.4.6.4

Return or Destruction of the Test Article

Research cigarettes: Participants will be instructed to return all research cigarette packs at the next in-person visit, regardless of whether they are empty, unopened or partially used. Any unused research cigarettes that are returned from the participant at the end of the study will be destroyed on site according to the general policy for drug disposal by the Investigational Drug Pharmacy.

E-cigs: Participants will be instructed to return all used and unused e-liquid pods to the study at each in-person visit to monitor use. We will ask participants to return the e-cig to the study site at the last in person visit and we will dispose of it on-site. Any unused pods that are returned at the last in person visit will be destroyed on site according to the general policy for drug disposal by the Investigational Drug Pharmacy.

Procedures during COVID-19:

Participants will receive a pre-paid envelope at Visit 7 to return all of their unused pods and e-cig to the study site. Any unused pods and e-cigs will be destroyed on site according to the general policy for drug disposal by the Investigational Drug Pharmacy.

7.4.6.5

Prior and Concomitant Therapy

Concomitant medications will be collected at baseline and regularly throughout the trial to monitor participant health conditions.

Participants taking varenicline, bupropion or nortriptyline as a smoking cessation medication in the prior month will be excluded from the study. Participants taking bupropion or nortriptyline for depression management and who expect to continue use of the medication throughout the trial will be eligible to participate. Additionally, participants who are prescribed bupropion or nortriptyline for depression management at any point during the study will be eligible to continue with the study. Medications related to certain medical conditions that are exclusions to the study, such as COPD and current heart conditions, will serve to alert the study staff of the presence of these conditions during screening. Once the participant is entered into the randomized double blind phase of the study, there are no other medications that will interfere with the participant's ability to participate.

8.0 Subject Numbers and Statistical Plan

8.1 Number of Subjects

We plan to enroll 300 participants in order to randomize 240 participants (60 in each of the four study arms).

8.2 Sample size determination

For the sample size calculation, we have used data for completers of our recent randomized controlled trial(8) to estimate magnitude of effects for the primary endpoint (NNAL, pmol/mg creatinine). Additionally, we have used data from Donny et al.'s trial [Table Supplement 15] (5). Based on their paper, the difference in log NNAL between the 0.4 mg/g group (sample size 96) and the 15.8 mg/g group (sample size 100) is $\log(0.78) = -0.248$ with a confidence interval of $\log(c(0.64, 0.96)) = (-0.446, -0.0408)$. Based on this, the within group standard deviation of log NNAL is 0.562. Combining the above two datasets, we shall assume that the effect size is 58% of the size of the standard deviation in the sample size calculation, slightly larger than reported above because our trial will have 16 weeks of follow-up. Let arm 3 of the trial be the group to which arms 1, 2 and 4 will each be compared. To adjust for multiple comparisons, the type one error level alpha is taken to be $.05/3=0.017$. The sample size of 60 subjects in each of the 4 arms is needed to provide 80% power of detecting a difference between any three arms and arm 3. In addition this trial will have over 95% power, at a 5% type 1 error rate, to detect the same effect on abstinence found in our recent RCT of VLNCs one month after the end of the randomized phase (20.2% in those randomized to VLNCs vs. 6.4% in those randomized to NNCs).

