3.3.2 Follow-up for withdrawn subjects

If participants are withdrawn from the study for any of the reasons noted above prior to randomization, they will be replaced until a total of 240 participants have been randomized to the study. Subjects who withdraw themselves or are withdrawn from the study at a visit will be asked to complete the study visit including a questionnaire regarding the reasons for dropping out.

For participants who withdraw themselves from the study, they will be asked if we can follow up with them at the week 16 visit. We will contact them via one call, message, and letter to complete the week 16 visit. If they wish not to be contacted to complete the week 16 visit, they will not be contacted.

If participants are lost to follow-up (i.e. simply do not respond to calls or letters without formally withdrawing) one final attempt will be made to contact them for the week 16 visit via one call, message and letter. If they complete the week 16 visit they will also be invited to the final (week 20) visit.

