Intent-to-treat (ITT) principle will be adopted for the analyses in both approaches. Additionally, the measurements of tobacco use and addiction and measurements of mental health will be monitored and summarized, and will be compared across these arms in a similar statistical fashion as described above. Self-reported compliance will be reported for all participants. For participants in arm 4 (VLNC plus placebo ecigs) their compliances will be further evaluated using biomarkers. Comparison on the outcome variables will be made between compliers vs non-compliers within arm 4 participants only. All analyses will be conducted using statistical software SAS version 9.4 or higher (SAS Institute, Cary, NC, USA) and R Programming language version 3.6.1 or higher (R Foundations). All tests will be two-sided and the statistical significance level to be used is 0.05.

Adjusted models will evaluate the treatment effect while adjusting for covariates, such as gender, age, race, SDOH scoring, and other baseline factors.

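### The stated 80% power for NNAL uses a partly completer-based effect on all 60 randomised per arm, with no allowance for leavers, although the declared analysis is intent-to-treat

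*Combined protocol and SAP*

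**What the plan says.** Section 8.2 builds the NNAL effect from two sources. For the first, "we have used data for completers of our recent randomized controlled trial(8) to estimate magnitude of effects for the primary endpoint"; the estimate itself is not given. The second is a published trial of reduced-nicotine cigarettes, where "the difference in log NNAL between the 0.4 mg/g group (sample size 96) and the 15.8 mg/g group (sample size 100) is" log(0.78) = -0.248 and "the within group standard deviation of log NNAL is 0.562". The population analysed in that trial is not stated. After combining them, "we shall assume that the effect size is 58% of the size of the standard deviation in the sample size calculation", a value described as "slightly larger than reported above because our trial will have 16 weeks of follow-up". Arm 3 is to be compared with each of arms 1, 2 and 4, and "the type one error level alpha is taken to be $.05/3=0.017". The section concludes that 60 per arm gives 80% power.

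Section 8.1 makes clear that 60 per arm is the number randomised. The margin between 300 enrolled and 240 randomised covers losses before randomisation, and section 3.3.2 replaces only withdrawals at that stage.

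On the analysis, section 8.3 compares week-16 NNAL by ANCOVA with the visit 3 value as covariate, makes all tests two-sided, and adds: "Intent-to-treat (ITT) principle will be adopted for the analyses in both approaches". It gives no rule for a missing week-16 NNAL. Section 3.3.2 seeks week-16 data from participants who withdrew themselves and agree to contact: "We will contact them via one call, message, and letter to complete the week 16 visit". Participants lost to follow-up get one final attempt of the same kind. No week-16 recall is described for those whom the investigator withdraws.

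**The concern.** Completers are people who stayed to the end. An intent-to-treat comparison at week 16 is meant to include people who stopped the assigned products, and section 3.3.2 actively seeks them. Someone who has gone back to a usual brand may show little of the effect of the assigned cigarette. Someone who cannot be reached has no week-16 urine. Either outcome lowers power relative to a calculation that gives all 60 per arm the full effect. The only adjustment that section 8.2 describes is upward.

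NNAL is the primary endpoint, and a null or borderline result will be judged against the printed 80%. If that figure describes a better-retained group than the one analysed, readers will put more weight on a null result than it can bear.

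**Working it through.** **Inputs from the documents.** Effect d = 0.58 SD, n = 60 per arm, alpha = .05/3 (section 8.2); two-sided tests, ANCOVA and intent-to-treat (section 8.3). The SD of 0.562 is taken as printed. The loss rate and the baseline correlation are not in the documents and are assumed below.

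**1. The plan's own figure.** The normal approximation is power = Φ(d·√(n/2) − z), with z = 2.394 for two-sided .05/3.

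- 0.58 × √30 = 3.177; 3.177 − 2.394 = 0.783; Φ(0.783) = 78.3%.
- With alpha rounded to 0.017 the result is 78.5%. The exact noncentral t gives 77.2%.
- The n for 80% is 2(2.394 + 0.842)²/0.58² = 62.2, so 63 per arm (62 at alpha 0.017).

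The stated 80% is thus reproduced to within 2 points by the approximation, but only with all 60 per arm measured and the full 0.58 SD. The t test needs 0.598 SD for 80% at 60 per arm. The printed figure contains no allowance.

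**2. Weight of the completer data.** On the plan's SD, the published trial alone gives 0.248/0.562 = 0.44 SD, which is about 50% power at 60 per arm. The step from 0.44 to 0.58 SD therefore comes from the completer data and the follow-up uplift.

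**3. Assumed loss q after randomisation.** Two extremes, by noncentral t:

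- Leavers missing: n = 60(1 − q), d = 0.58.
- Leavers all measured and showing no effect: n = 60, d = 0.58(1 − q).

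For ANCOVA, d is divided by √(1 − ρ²), where ρ is the correlation of baseline with week 16. This applies only if 0.562 is not already a baseline-adjusted SD, which section 8.2 does not say. The last column is the ρ that restores 80%, from ρ² = 1 − (d/d80)². Here d80 is the effect that the t test needs: 0.598 at n = 60, 0.631 at 54, 0.671 at 48.

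| Scenario | n per arm | d | Unadjusted | ρ = 0.3 | ρ = 0.5 | ρ for 80% |
|---|---|---|---|---|---|---|
| No loss, full effect | 60 | 0.580 | 77% | 82% | 89% | 0.24 |
| 10% missing | 54 | 0.580 | 72% | 77% | 85% | 0.39 |
| 20% missing | 48 | 0.580 | 66% | 71% | 80% | 0.50 |
| 10% measured, no effect | 60 | 0.522 | 67% | 72% | 81% | 0.49 |
| 20% measured, no effect | 60 | 0.464 | 55% | 59% | 69% | 0.63 |

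If half the leavers are recalled with no effect and half are missing, unadjusted power is 69% at 10% loss (57 per arm, 0.549 SD) and 60% at 20% (54 per arm, 0.516 SD).

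**4. Data used elsewhere in the same section.** The abstinence rates of 20.2% and 6.4% equal 19/94 and 6/94. The denominator of 94 is the number randomised per group in the earlier trial (section 2.2). For that endpoint, section 8.2 appears to use all-randomised data; for the primary endpoint it uses completers.

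**The case against.** The case against is substantial.

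- **No arithmetic error.** The 80% is reproduced within 2 points. Part of the gap between 77% and 80% is only t test versus approximation. This stands: the issue is a planning assumption.
- **0.58 SD is a blend.** It mixes completers with a published trial whose analysis population is unstated, and then adds an uplift. Nor are completers the same as people using only the assigned product: section 2.2 separates completers from exclusive users of the research cigarettes and found very similar results in both. Multiplying the blended effect by an on-product fraction may therefore count some dilution twice. This stands, although the section 2.2 results do not list NNAL and do not compare completers with all randomised participants.
- **No effect in leavers is an extreme.** Some may have quit or cut down; section 2.2 reports more quitting in the reduced-nicotine group (18% vs 4%). Recall is also light, so many leavers would be missing rather than diluted. This stands as to size, but missing leavers lower power too.
- **Arm 3 versus arm 4.** Both smoke VLNC cigarettes, so a return to normal-nicotine cigarettes does not explain dilution there. Any dilution would have to come through the e-cigarette. This stands.
- **ANCOVA may compensate.** With ρ = 0.5 the shortfall disappears at 10% loss. This stands as a possibility, but section 8.2 states neither a correlation nor a gain from adjustment.

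A reader might infer that true power is below 80% by a known amount, such as 67%. The documents do not support that: they give no loss rate, no off-product share, and neither a completer nor an all-randomised NNAL effect.

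**Conclusion.** The point holds as a mismatch between the stated power and the declared analysis. The effect rests partly on completers, is adjusted only upward, and is applied to all 60 randomised per arm with no allowance for leavers. The plan's inputs give 77% to 78% with nobody lost or diluted. The stated 80% therefore cannot absorb any loss unless baseline adjustment compensates, and section 8.2 does not show that it does.

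The direction of the effect on unadjusted power assumes that leavers are either missing or show a smaller effect. If every leaver were measured and kept the full effect, power would stay at 77% to 78%. The size is unknown. Across assumed losses of 10% to 20%, it runs from 55% (20% measured with no effect, unadjusted) to 85% (10% missing, ρ = 0.5). It would also go too far to say that the 80% belongs to a completer population, because the 0.58 SD comes only partly from completers.

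**What to change.** In section 8.2:

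1. Re-estimate the NNAL effect from all randomised participants with week-16 NNAL in the sponsor's earlier trial. If that cannot be done, label 0.58 SD as a completer-based effect.
2. State the expected loss after randomisation, the baseline correlation, and whether the SD of 0.562 is already baseline-adjusted.
3. Restate power at 60 per arm under the declared intent-to-treat ANCOVA as a range over plausible loss, covering leavers who are missing and leavers who are measured with a reduced effect.
4. Treat arm 3 versus arm 4 separately, with its own assumed effect.

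Keep 240 randomised, and do not enter 67% or any other single figure from the table as the trial's power. The cost is one recalculation, mainly from the sponsor's own earlier trial, and a reworded paragraph. The design and the analysis are unchanged; the stated power may become less favourable.

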Phone call, text, and email reminders will be used throughout the study to remind participants of their next visits (approximately 1-2 days prior). Also, visit time/date confirmation and study center directions will be emailed/mailed to the participant prior to Visit 1 (see First Appointment Reminder document). For participants who allow us to contact them through phone and text messaging, the study team will be using Google Voice to call or text participant reminders of the study visit and reminders to complete the study surveys with the REDCap survey link. Google Voice is phone service that allows researchers to communicate with participants without revealing their personal phone numbers. The study team will save participants phone number with their study ID. Participants will be told not to share PHI through this phone number.

Biospecimen Processing

All urine samples collected will be stored and analyzed in the project biomarkers core lab led by [name].

Data Collection via Phone

If participants are unable to attend an in-person study visit, the researcher will attempt to collect data over the phone. Participants will not be compensated for data provided through this method.

Missed Visit Procedures

Participants will be called at least once to reschedule a missed Visit 1. For participants who do not show up for any other in-person visit, up to 3 phone/email attempts will be made to contact them to reschedule their appointment.

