8.3 Statistical methods

Basic baseline statistics including means (standard deviations) and frequency distributions (percentages) will be reported for demographic characteristics, smoking characteristics, nicotine dependence, and nicotine and toxicant exposure. Characteristics will be reported by the four treatment arms to identify treatment arm imbalances. Numerical baseline characteristics will be compared among four arms using ANOVA tests or nonparametric Kruskal-Wallis tests when appropriate. Categorical variables will be compared using chi-square tests or Fisher's exact tests. The focus of the statistical analysis will be the difference between four trial arms in terms of the biomarkers of toxicity and health effects. Analyses will be conducted in two approaches, which will address our research questions in two different angles. The first approach is a simplified and streamlined one, the longitudinal measurements of these biomarkers over the 16-week period will be summarized by using just the baseline (visit 3, pre-randomization) and final (visit 7, end of randomization period) measurements. Analysis of Covariance (ANCOVA) models will be used to compare the final measurements among the four arms, while the baseline measurements will be treated as controlled covariates in the model. Specifically, the comparisons between arms 1 and 3 and between arms 2 and 4 answer whether switching to very low nicotine cigarettes leads to lower markers of harm as compared to continuing on normal nicotine cigarettes. This addresses specific Aim 1. Furthermore, we will study if this reduction is the same when combined with 5% nicotine e-cigs (arms 1 and 3) and combined with placebo e-cigs (arms 2 and 4). Similarly, comparison between arm 1 and arm 2 reveals if access to nicotine versus placebo e-cigs impacts these biomarkers. This will address Aim 2. In particular, we will test if the arm 3 has the best outcome as stipulated in Aim 2. These analyses will be conducted using ANCOVA models with interaction terms between traditional cigarettes (normal nicotine vs. very low nicotine) and e-cig (5% vs. 0%). Appropriate transformation may be done on some of the outcome variables (for example log-transformation) to make sure the underlying statistical assumptions are all satisfied. Note that for NNAL, one of our main biomarkers of toxicity; it can only be analyzed using the first approach due to the limitation of number of measures.

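### The 80% power stated for each NNAL comparison with arm 3 is slightly optimistic with complete week-16 data and makes no allowance for loss after randomisation

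*Combined protocol and SAP*

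**What the plan says.** Section 8.2 sizes the trial on log NNAL. Arm 3 is compared with each of arms 1, 2 and 4, so alpha is set at .05/3, written as 0.017. On the effect, the authors "assume that the effect size is 58% of the size of the standard deviation in the sample size calculation". On the spread: "Based on this, the within group standard deviation of log NNAL is 0.562". The conclusion is: "The sample size of 60 subjects in each of the 4 arms is needed to provide 80% power".

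Section 8.1 gives the numbers recruited: "We plan to enroll 300 participants in order to randomize 240 participants (60 in each of the four study arms". Under section 3.3.2, participants withdrawn "prior to randomization, they will be replaced until a total of 240 participants have been randomized to the study". The same section goes on to plan one week-16 contact attempt for participants who withdraw themselves (unless they decline) and for those lost to follow-up. It gives no expected rate for either.

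Section 8.3 makes all tests two-sided. It analyses NNAL by ANCOVA on the visit 7 value, "while the baseline measurements will be treated as controlled covariates in the model", and says that NNAL has too few measurements for the longitudinal models. For a missed in-person visit, section 7.2 says: "If participants are unable to attend an in-person study visit, the researcher will attempt to collect data over the phone".

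**The concern.** The number that section 8.2 calls needed for 80% power is the number randomised, so the claim holds only if every randomised participant contributes a week-16 NNAL value. The plan itself expects some not to: it lists many reasons for withdrawal, sets out a recontact procedure, and takes its own-trial effect from completers. NNAL is more exposed than the questionnaire outcomes, because a phone contact cannot supply the visit 7 urine sample.

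In addition, the stated inputs do not quite reach 80% with complete data.

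What is at stake is how a null pairwise result on the primary endpoint is read. A reader would take it to come from a comparison with 80% power, when the power on the stated inputs is somewhat lower and falls with each missing sample.

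**Working it through.** **Inputs**

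- Effect d = 0.58 in SD units (section 8.2). The SD of 0.562 cancels.
- Alpha .05/3 = 0.01667, printed as 0.017 (section 8.2), two-sided (section 8.3).
- 60 randomised per arm (section 8.1), allocated 1:1:1:1 (section 7.4.3).
- Losses after randomisation of 10% and 20% are assumptions, because the documents print no rate. They leave 54 and 48 analysed per arm.

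**Step 1. The plan's own figure, 60 per arm**

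Normal approximation: power = Φ(d·√(n/2) − z), where z is the two-sided critical value.

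- d·√(n/2) = 0.58 × √30 = 3.177.
- Alpha .05/3: z = 2.394, so Φ(0.783) = 78.3%.
- Alpha 0.017 as printed: z = 2.387, so Φ(0.790) = 78.5%.
- Noncentral t, 118 df, alpha .05/3: 77.2%. With the error variance pooled over four arms: 77.7%.
- Dunnett critical value of 2.348, which section 8.2 does not specify: Φ(0.829) = 79.6%.

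Number per arm for 80%: n = 2(z + 0.842)²/d². At .05/3 this is 2 × 3.236²/0.3364 = 62.2, so 63. At 0.017 it is just under 62, so 62. The t version at .05/3 needs 64.

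**Step 2. Fewer analysed, no baseline-adjustment gain**

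| Analysed per arm | d·√(n/2) | t, .05/3 | Normal, .05/3 | Normal, 0.017 |
|---|---|---|---|---|
| 60 (complete) | 3.177 | 77.2% | 78.3% | 78.5% |
| 54 (assumed 10% loss) | 3.014 | 71.9% | 73.2% | 73.5% |
| 48 (assumed 20% loss) | 2.841 | 65.7% | 67.3% | 67.5% |

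A Dunnett critical value would give about 75% at 54 and 69% at 48.

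**Step 3. What the planned ANCOVA could recover**

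If 0.562 is an unadjusted SD, adjusting for a baseline with correlation ρ raises the effective effect to 0.58/√(1 − ρ²). At .05/3 with the t distribution and 2n − 3 df, the results are:

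| Analysed per arm | ρ needed for 80% | Power at assumed ρ = 0.3 | Power at assumed ρ = 0.5 |
|---|---|---|---|
| 60 | 0.24 | 81.5% | 89.0% |
| 54 | 0.40 | 76.5% | 85.0% |
| 48 | 0.50 | 70.5% | 79.8% |

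Check of the first row: 0.58/√(1 − 0.244²) = 0.598, which is the effect detectable with 80% power at 60 per arm. The normal approximation needs slightly lower correlations: 0.19, 0.36 and 0.48.

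**The case against.** The strongest reply is that the planned analysis can absorb the gap. Section 8.3 specifies ANCOVA with baseline NNAL as covariate, and leaving that gain out of a sample size calculation is a common conservative choice. A correlation of 0.5 would hold power at about 80% even with 20% loss. This stands as a possibility. It cannot be credited as the text is written, because section 8.2 claims no such gain, gives no correlation, and does not say whether 0.562 already reflects baseline adjustment. If it does, the gain cannot be counted twice.

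It is also fair that the loss rates are assumed and that the plan works to limit loss, with week-16 recontact and up to three rescheduling attempts. The use of completers from the earlier trial shows which data were used and does not give a rate. What stands without any assumed rate is that section 8.2 makes no allowance at all.

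A reader might infer from the complete-data figure that the sample size contains a serious arithmetic error. The documents do not support that. The shortfall is one and a half to three percentage points, or two to four participants per arm, and a Dunnett critical value gives 79.6%.

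A reader might also infer that 0.58 SD is wrong, because the one source with printed figures gives 0.248/0.562 = 0.44 SD. But section 8.2 says that 0.58 draws on two datasets and a longer follow-up, and the own-trial NNAL result is not printed. Likewise, no printed figure supports 0.58 for arm 3 against arm 4, and the level of the interval behind 0.562 is unstated. These are missing details, and none of them shows an error.

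**Conclusion.** The point holds in a limited form. On section 8.2's own inputs, pairwise power is about 77% to 78.5% with complete week-16 NNAL, so the stated 80% is slightly optimistic. The main weakness is that nothing is allowed for missing week-16 urine after randomisation: each lost sample takes power further below the stated figure unless baseline adjustment makes it up. The size is 72% to 73.5% at 10% loss and 66% to 67.5% at 20%. Both rates are assumptions, and both results exclude any covariate gain.

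It would go too far to conclude that the trial is underpowered as it will be analysed. A moderate baseline correlation would restore 80% if 0.562 is unadjusted, and the documents do not settle either matter. The conclusion is that the stated power is not supported as written, and that it should be corrected because it concerns the primary endpoint and costs little to put right.

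**What to change.** Revise section 8.2 and leave enrolment unchanged.

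- Restate the pairwise power as about 78% with complete week-16 data at 0.58 SD and alpha .05/3.
- Give the power also at the number per arm expected to have a week-16 NNAL value, with the retention assumption stated.
- If the ANCOVA gain is relied on to reach 80%, compute power for that analysis, state the assumed baseline correlation, and say whether 0.562 is already baseline-adjusted.

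The cost is protocol wording only, with no extra participants and no change to design or analysis. The downside is a slightly less favourable stated power.
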